### 3C.6. Randomized Trial Evaluating *B-SMART* (Specific Aim 4; Months 8-24)

**3C.6.1. Experimental Design.** The *B-SMART mobile web app* will be evaluated in a randomized pretest-posttest controlled design. In months 6-11, first time DWI offenders and CFMs will be recruited for participation in the trial. First-time DWI offenders and their CFMs will be randomized together to the intervention (*B-SMART*)

(n=150) or a usual and customary (UC) IID information condition comparison group (n=150) following baseline assessment. Assessment via web-based surveys will be conducted with the DWI offenders and CFMs at baseline, 3-month follow-up, and 9-month follow-up

post randomization. Also, information on frequency of alcohol-positive IID tests (termed “lockout events”) will be acquired by the project from the Santa Fe County and Municipal DWI Program at the 9-month assessment point (posttest only) for each DWI offender. Thus, the proposed efficacy trial (see **Figure 5**) will be a 2 (level of treatment – app intervention vs. UC information) x 3 (level of time – baseline vs. 3-month follow-up vs. 9-month follow-up) mixed factorial design. Baseline and follow-up data collection will be conducted via online surveys and a customized web portal and include DWI offender and CFM alcohol frequency and use measures and measures of family communication and functioning (see 3C.7). Participants will fill out a locator form with contact information and collateral contact information to locate them for assessment at the 3-month and 9-month follow-ups. We have employed these locator procedures in prior trials, keeping average loss across 9 months at 15%-20%. Cumulative IID lockout event data will be collected for all DWI offenders from the Santa Fe County DWI Program at the 9-month assessment point.

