### 3C.3. Target Population

[figure not shown]
The project has two relevant, linked target populations: 1) CFM of DWI offenders and 2) the first-time DWI offenders themselves. The CFM is the primary user of the *B-SMART mobile web app* and content will be tailored toward them, with supporting information provided for the DWI offender.

Participants in both the web app development phase (Months 1-7) and the randomized efficacy trial phase of the project (Months 7-24) will be recruited from the Santa Fe County DWI Program, the county-wide program that manages probation and sentencing programs and requirements for all DWI offenders in Santa Fe County, New Mexico. In New Mexico, Santa Fe County had the fourth-highest ranked number of first time DWI offenders (360) in 2015 and 313 first time convictions in 2016. Participants in the development phase will not be eligible for the randomized trial phase of the project. **Figure 3** displays the inclusion and exclusion criteria for participation in either phase of the investigation.

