**FIGURE 5: Randomized Efficacy Trial Design**

Time	Experimental Group (randomized)	
	B-SMART Intervention Group N=150 DWI Offenders & CFM	Usual & Customary Information Group N=150 DWI Offenders & CFM
Baseline	study cohort assessment	study cohort assessment
Web App Intervention	YES	NO
3-month Follow-up Post-test	study cohort assessment	study cohort assessment
9-month Follow-up Post-test & IID Data Collection	study cohort assessment	study cohort assessment

**3C.6.2. Recruiting and Consenting Procedures.** Potential participants will be contacted for recruitment and consenting at monthly Santa Fe County DWI Program meetings held for each DWI offender at the beginning of her/his probation period. CFMs of first-time DWI offenders will be contacted via email and a web recruitment portal designed exclusively for the project and followed up with a recruitment phone call.

Participants will only be enrolled in the trial if **both** the DWI offender and CFM consent to participate. Our previous work in Phase I of the project found a strong willingness to participate in the project among both DWI offenders and CFMs based on their interest in better family functioning and the unique convenience of a *B-SMART mobile web app* that could be beneficial to their experiences with the IID.

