**3C.6.5. Sample Size Determination.** The sample size for the randomized trial in the Phase II research is designed to provide sufficient information for Phase III commercialization. The sample size assumes the counts of interlocks are Poisson distributed. We have assumed 4 interlocks over 9 months in the control arm or a rate of 0.44 per month for each DWI offender. In the *B-SMART mobile web app* group, we have assumed a reduction of 40% from 0.44, resulting in a rate of 0.27 per month. The null hypothesis is that the ratio of these two rates is 1.0 versus 0.6. Assuming a Type I error of 0.05 (2-sided), 90% power, sample size is only 27 DWI offenders per group. However, if the rate is higher up to 1 per month, the sample size required declines since the percent reductions yield wider absolute differences in the rates. We also are keen to know the reductions achievable with the *B-SMART* group, so we evaluated the sample size with regards to other effect sizes. A Cochrane meta-analysis reported the impact of IIDs to reduce risk by 64%, but with a confidence interval that ranged from 76% to 37%. In the proposed trial, we have two treatment groups and may see less impact than that in the meta-analysis. Thus, a sample size of 119 DWI offenders per group will allow for 90% power with a comparison of 0.44 to 0.36 or approximately a 20% reduction in interlocks. We will adjust for an expected 15% attrition and this sample size also has sufficient sample size to evaluate the impact in various gender and ethnic subgroups. Thus, we propose to randomize 150 DWI offenders and 150 CFMs to each arm of the trial.

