#### DWI Offender:

- male or female
- 21 years or older
- first-time DWI offender with IID installed in vehicle
- enrolled in Santa Fe County DWI Program
- have a smartphone, tablet computer, or personal computer with Internet access
- consent to participate
- able to read and speak English or Spanish

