## **2.4. INCLUSION OF WOMEN, MINORITIES, AND CHILDREN**

### **Inclusion of Women and Minorities**

Potential participants will not be excluded based on ethnic group or race. We will attempt to recruit participants at similar rates to the 2014 New Mexico DWI Offender Characteristics and Recidivism Report. According to the Report, the race/ethnicity of the DWI offender population in New Mexico from 2003 through 2013 were as follows: 49% Hispanic, 28% White, 20% American Indian/Alaska Natives, and 3% African American. The gender of the DWI offender population was 72% male and 28% female. The Targeted Enrollment Table represents a composite of these numbers.

During the recruitment process, the UNM project coordinator will screen for participants using IRB-approved protocols for screening based on gender, race, and ethnicity. If the project coordinator finds that we are over-recruiting a particular gender or racial or ethnic group, we will place them on a waiting list until we have recruited an adequate number of targeted participants

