### **Inclusion of Children**

[figure not shown]
Children under 18 will be ineligible for participation. Children under 18 will not be enrolled in the proposed project because this app is aimed at adults. We are limiting age to no younger than 21 years old because DWI offenders under age 21 fall under a different set of laws and court programs than offender 21 or older. To keep things simple, we will also limit the age of CFMs to 21 years or older. Age will be self-reported by the participants.

Human Subjects oversight will be conducted by the Western Institutional Review Board (WIRB; DHHS IRB Reg. No. 00000533). The IRBs will approve all consenting procedures (including recruitment advertisements, posters, recruitment letters and consent forms), intervention protocols, survey instruments and data collection protocols, and data management procedures prior to study implementation and prior to the recruitment of any participants.

The investigative team has extensive experience from previous community-based trials and as a result already have a rich inventory of recruiting materials and protocols to be used for this study, including materials and protocol used to recruit DWI offenders and CFMs to the Phase I research. We will recruit 300 eligible DWI offenders and 300 eligible CFMs to complete the baseline assessment and be randomized. That way, at least 255 DWI offenders and 255 CFMs will complete the 9-month follow-up (85% retention).

Potential participants will be contacted for recruitment and consenting at monthly Santa Fe County DWI program meetings held for each DWI offender at the beginning of her/his probation period. CFMs of first-time DWI offenders will be contacted via email and a web recruitment portal designed exclusively for the project and followed up with a recruitment phone call. Participants will only be enrolled in the trial if both the DWI offender and CFM consent to participate. Our previous work in Phase I of the project found a strong willingness to participate in the project among both DWI offenders and CFM based on their interest in better family functioning and the unique convenience of a *B-SMART mobile web app* that could be beneficial to their experiences with the IID. In New Mexico, Santa Fe County had the fourth-highest ranked number of first time DWI offenders (360) in 2015 and 313 first time convictions in 2016.

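### Recruiting 300 offender-family dyads in six months needs about 1.7 to 1.9 times the offender flow the plan documents; at that flow, power for the 20% reduction is 75-81%, not 90%

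*Combined protocol and SAP*

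**What the plan says.** - **Window.** Section 3C.6.1: "In months 6-11, first time DWI offenders and CFMs will be recruited for participation in the trial".
- **Target.** Section 2.5 (Recruitment and Retention Plan): "We will recruit 300 eligible DWI offenders and 300 eligible CFMs to complete the baseline assessment and be randomized". Section 3C.6.5 splits this as 150 dyads per arm.
- **Source and point of contact.** Section 3.1.A draws all participants from the Santa Fe County DWI Program. Section 3C.6.2 places the approach at "monthly Santa Fe County DWI Program meetings held for each DWI offender at the beginning of her/his probation period", and enrols a pair only if both members consent. The eligibility list in section 2.2 asks only that the offender be "enrolled in Santa Fe County DWI Program".
- **Supply.** Section 3C.3, repeated in section 2.5: "Santa Fe County had the fourth-highest ranked number of first time DWI offenders (360) in 2015 and 313 first time convictions in 2016". No uptake rate, count of offenders already on probation, or second site is given.
- **Quotas.** Section 2.4, on a gender, racial or ethnic group that is being over-recruited: "we will place them on a waiting list until we have recruited an adequate number of targeted participants".
- **Power.** Sections 3C.6.5 and 4.4 and the SAP: "a sample size of 119 DWI offenders per group will allow for 90% power with a comparison of 0.44 to 0.36". The size is then raised for 15% attrition.
- **Outcome data.** Section 3C.6.1: "Cumulative IID lockout event data will be collected for all DWI offenders from the Santa Fe County DWI Program".
- **Project months.** The trial phase is months 7-24 in section 3C.3 but 8-24 in sections 3C.2 and 3C.6. Recruitment starts in month 6, and section 3C.6.3 places implementation in months 7-11.

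**The concern.** The recruitment plan cites the two annual counts in support of feasibility, yet 300 dyads in six months nearly equals, in half a year, what those counts give for a whole year. The shortfall appears before any loss to ineligibility, refusal by either member, or lack of a qualifying family member.

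What is at stake is the ability to detect the smaller effect. The plan needs only 27 per group for a 40% reduction; it goes to 150 per arm because it wants 90% power for about 20%. If accrual falls to what the supply figures support, that is the claim that fails. Found in month 11 of a 24-month project with nine months of follow-up, the shortfall would leave little room to recover.

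**Working it through.** **Inputs.** Annual supply 313 or 360 (section 3C.3), used as proxies for program entries. Window months 6-11, six months counted inclusively. Control mean 4 lockouts over 9 months, Poisson counts, two-sided 5% level (section 3C.6.5). Allocation 1:1.

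**1. The plan's own sizes.** With rate ratio RR and control mean 4, the variance of the log rate ratio at n per arm is (1/4 + 1/(4 RR))/n, so for 90% power

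n = (1.960 + 1.282)² × (1/4 + 1/(4 RR)) / (ln RR)².

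- RR 0.8: 10.507 × 0.5625 / 0.2231² = 118.7, so 119 (plan: 119).
- RR 0.6: 10.507 × 0.6667 / 0.5108² = 26.8, so 27 (plan: 27).

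Both reproduce, so the formula is a fair yardstick. It takes the reduction as exactly 20%; the printed rates 0.44 and 0.36 are an 18% reduction and would need 147 per group.

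**2. Supply against target.**

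- Monthly flow: 313/12 = 26.1; 360/12 = 30.0. Needed: 300/6 = 50.
- Six months: 156.5 to 180 offenders.
- Uptake needed for 300 dyads: 300/180 = 167% to 300/156.5 = 192%.
- Dyads without a documented source: 300 − 180 = 120 to 300 − 156.5 = 143.5. Against 2 × 119 = 238, the gap is 58 to 81.5.

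**3. Power for a 20% reduction at that flow.** Power = Φ(|ln RR| / √Var − 1.960). For example, at 90 per arm √(0.5625/90) = 0.0791, and Φ(0.2231/0.0791 − 1.960) = 0.806.

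| Dyad uptake, months 6-11 | n per arm | Power, complete records |
|---|---|---|
| 100% | 78.25 to 90 | 0.749 to 0.806 |
| 75% (assumed) | 58.7 to 67.5 | 0.625 to 0.686 |
| 50% (assumed) | 39.1 to 45 | 0.461 to 0.514 |

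A simulation at 78 and 90 per arm gave 74.9% and 80.8%. With 15% lost at 100% uptake (66.5 to 76.5 per arm), power is 0.680 to 0.740. Complete records are the more relevant case, because the outcome comes from the program's database.

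**4. Detectable reduction at 90% power, 100% uptake.** 22.8% to 24.4% with complete records; 24.6% to 26.3% with 15% attrition.

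**5. The 40% scenario.** At 50% uptake, power is 0.975 to 0.987 with complete records and 0.950 to 0.972 with attrition.

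**6. Longer windows, 20% reduction, complete records.**

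| Recruitment | Dyads at 100% uptake | Power at 100% | Power at 50% | Last 9-month point (end of month) |
|---|---|---|---|---|
| Months 6-12 | 183 to 210 | 0.811 to 0.862 | 0.520 to 0.578 | 21 |
| Months 6-13 | 209 to 240 | 0.860 to 0.903 | 0.575 to 0.635 | 22 |
| Months 6-14 | 235 to 270 | 0.897 to 0.933 | 0.625 to 0.686 | 23 |

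If month 24 is kept for the one-month analysis, this leaves two months, one month and no time for late surveys respectively.

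**The case against.** - **The 90% is not a misstatement.** The plan attaches it to 119 per group, and that reproduces. This stands: the defect is in the accrual that the size depends on, not in the power formula.
- **The counts are not program entries.** One counts offenders, the other convictions, and neither counts people entering the program. This is fair, so the shortfalls are approximate. But they are the plan's own feasibility evidence, and true entries would have to be 1.7 to 1.9 times higher to meet the target.
- **Offenders already on probation could be recruited.** Eligibility does not bar them, so the flow is not a hard ceiling. The plan does not, however, say they will be approached or how many there are.
- **Not all the material can be seen.** The timeline figure and a letter of support are not in the text under review and might help. What can be judged is the text, which gives no other supply figure.
- **The quota rule may not reduce total accrual.** True: its effect cannot be quantified. It adds a constraint and brings in no one.
- **The loss is modest and causes no bias.** Too few participants does not inflate type I error, and the 40% alternative keeps its power. That limits the consequence to the smaller effect, which is the one used to choose 150 per arm.
- **Recruitment to month 14 would restore about 90% power.** It would give 90-93%, but only at 100% uptake with complete records and with no slack for late surveys, which carry the secondary outcome and the mediators.

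**Conclusion.** The concern holds and needs correcting before recruitment. On its own supply figures the plan can expect about 157 to 180 new offenders in the window, not 300, and power for the 20% reduction is then 75-81% rather than 90%.

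That range is favourable to the plan. It assumes 2015-2016 volumes persist, every new offender is eligible with a consenting family member, records are complete, counts are Poisson without overdispersion, and the reduction is a full 20%. On the printed rates 0.44 and 0.36 the power is 66-72%. The figures for 75% and 50% uptake rest on assumed rates, since the documents give none. A sufficient number of offenders already on probation, or a second source, would change the conclusion, but neither is documented. The differing month labels are a minor inconsistency that affects none of these calculations.

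**What to change.** 1. In sections 3C.6.1, 3C.6.5, 2.5 and 4.4 and in the SAP, restate n and power, or the detectable reduction, at attainable accrual with an explicit dyad uptake assumption. This is needed whatever else is done: at 50% uptake none of the windows in the table above exceeds 69% power.
2. Where the 24 months allow, extend recruitment from month 6 to month 12 or 13, and the implementation window in section 3C.6.3 with it. Month 14 is possible only if no time is kept for late surveys.
3. If offenders already on probation or another county are counted on, say so and give the number available.
4. Reconcile the trial-phase months in sections 3C.2, 3C.3 and 3C.6 with recruitment starting in month 6.

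**Cost.** Edits to wording and timeline, a less favourable stated size and power, and less slack before month 24. Months 6-13 reach 90% power only at the 360 figure with about 99% uptake (238/240) and complete records; at the 313 figure they give 86%. Adding offenders already on probation may bring in people with less interlock time remaining. The documents state no interlock term, so that effect cannot be sized here.

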**FIGURE 5: Randomized Efficacy Trial Design**

Time	Experimental Group (randomized)	
	B-SMART Intervention Group N=150 DWI Offenders & CFM	Usual & Customary Information Group N=150 DWI Offenders & CFM
Baseline	study cohort assessment	study cohort assessment
Web App Intervention	YES	NO
3-month Follow-up Post-test	study cohort assessment	study cohort assessment
9-month Follow-up Post-test & IID Data Collection	study cohort assessment	study cohort assessment

**3C.6.2. Recruiting and Consenting Procedures.** Potential participants will be contacted for recruitment and consenting at monthly Santa Fe County DWI Program meetings held for each DWI offender at the beginning of her/his probation period. CFMs of first-time DWI offenders will be contacted via email and a web recruitment portal designed exclusively for the project and followed up with a recruitment phone call.

Participants will only be enrolled in the trial if **both** the DWI offender and CFM consent to participate. Our previous work in Phase I of the project found a strong willingness to participate in the project among both DWI offenders and CFMs based on their interest in better family functioning and the unique convenience of a *B-SMART mobile web app* that could be beneficial to their experiences with the IID.

**3C.6.3. Implementation of *B-SMART Mobile Web App*.** *B-SMART* will be implemented with first-time DWI offenders and CFM randomized to the intervention in months 7-11. Following the baseline survey, a link will be presented to the participants where the *B-SMART mobile web app* can be accessed through their web browsers on their smartphones, tablet computers, or personal laptop/desktop computers. This link will also be sent to their email addresses and by text message to their mobile phones. A customized backend SQL database will track participants' progress through the mobile web app. Unique identifying user codes will be assigned to all first-time DWI offenders and their CFM by the research staff; participants will select their own password under the user profile section of the web app. The User ID and password will be used to access *B-SMART* and mark the usage data in the SQL database (see description of Server-side Process Measures in Section 3C.7.3). In case users forget their password, they will provide a unique answer to a standard personal question (e.g., what is your mother's first name), and using this information, the mobile web app database will return the forgotten password. If users forget both their User ID and password, they can call or email a technical assistance hotline staffed by KB media developers.

Orientation to *B-SMART* will be primarily self-explanatory, which we will confirm in usability testing (see 3C.5.6). In our past research, nearly all adults were adept at using a web browser across devices, so we are confident that *B-SMART* and its use will take little explanation. To ensure use, we will: 1) design the mobile web app to be inherently interesting and enjoyable through our iterative development procedures incorporating user input (see C3.5.2); 2) make the user navigation simple and easy to browse so modules can be viewed quickly; 3) create a mobile web app that can be completed in no more than 120 minutes to avoid boredom that provokes drop out; 4) program the mobile web app so its interface is optimized on a variety of technology platforms (smartphone, tablet computer, or personal computer) to accommodate the preferences of any user; and 5) engineer low and high bandwidth versions of the mobile web app that automatically adjust to the user's bandwidth access. While connectivity data in 3C.5.5 indicates sufficient broadband and cell coverage in New Mexico for the *B-SMART mobile web app*, this programming feature will allow the use of *B-SMART* even in limited connectivity situations. Reminders to use *B-SMART* (or read the IID Information pamphlet in UC group, see 3C.6.3) will be sent to participants every 5 days for two weeks after randomization. If the either the mobile web app (or the web pamphlet in the UC group) still is not accessed, research staff will contact participants by telephone and encourage them to use it.

**3C.6.4. Usual and Customary IID Information.** Participants randomized to the usual and customary care (UC) group will receive a website with a pamphlet on the IID installed in their vehicle and the manufacturer information provided about the IID in PDF format, in both English and Spanish. This constitutes a UC group, as such pamphlets are widely distributed to DWI offenders who have IIDs installed in their vehicles. Thus, providing this pamphlet represents a standard information provision for first-time DWI offenders and their CFMs.

**3C.6.5. Sample Size Determination.** The sample size for the randomized trial in the Phase II research is designed to provide sufficient information for Phase III commercialization. The sample size assumes the counts of interlocks are Poisson distributed. We have assumed 4 interlocks over 9 months in the control arm or a rate of 0.44 per month for each DWI offender. In the *B-SMART mobile web app* group, we have assumed a reduction of 40% from 0.44, resulting in a rate of 0.27 per month. The null hypothesis is that the ratio of these two rates is 1.0 versus 0.6. Assuming a Type I error of 0.05 (2-sided), 90% power, sample size is only 27 DWI offenders per group. However, if the rate is higher up to 1 per month, the sample size required declines since the percent reductions yield wider absolute differences in the rates. We also are keen to know the reductions achievable with the *B-SMART* group, so we evaluated the sample size with regards to other effect sizes. A Cochrane meta-analysis reported the impact of IIDs to reduce risk by 64%, but with a confidence interval that ranged from 76% to 37%. In the proposed trial, we have two treatment groups and may see less impact than that in the meta-analysis. Thus, a sample size of 119 DWI offenders per group will allow for 90% power with a comparison of 0.44 to 0.36 or approximately a 20% reduction in interlocks. We will adjust for an expected 15% attrition and this sample size also has sufficient sample size to evaluate the impact in various gender and ethnic subgroups. Thus, we propose to randomize 150 DWI offenders and 150 CFMs to each arm of the trial.

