**FIGURE 4: Proposed Flow for *B-SMART* Web App**

how to support their family member, and promote positive shared experiences to support the DWI offender's abstinence. CFMs will be able to share content with the DWI offender. When appropriate, we will encourage the CFM to invite the DWI offender to participate in the activities together for shared learning. Working with KB's instructional designer and utilizing the design of the Phase I prototype, the team will create a fully-functional mobile web app with a learning-centric structure with content, activities, tools and exercises that are tailored for CFMs to maximize effective navigation for the user but allow a user to toggle settings to navigate all content. *B-SMART* will also be useful and functional for the first-time DWI offender and will be designed to be easily navigable and informative for both the CFM and offender. While our Phase I research developed these specifications, they will be validated in final form by the iterative development research for Phase II. Additional

features to be programmed will be considered during the formative research, based on feedback from participants. All app content will be available in both English and Spanish, based on user language preference. The Spanish translation/back-translation verification process will be managed by Project Coordinator [name] (KB), a native Spanish speaker, and assisted by Project Research Scientist [name] (UNM), a native Spanish speaker. A professional translator will also be utilized for back-translation.

**3C.5.2. Iterative Development Approach.** As with all effective digital designs, smartphone applications must be carefully and systematically designed, employing feedback and reviews from the intended target group (in this case, DWI offenders and their CFMs) in a series of repeated development cycles. We will employ a series of systematic app development steps used in prior smartphone application and website projects: 1) initial focus groups to review the proposed program flow and content (n=32); 2) usability testing sessions with CFM (n=16) and DWI offenders (n=16) of a beta version (near final) of *B-SMART* to ensure usability and navigability, and 3) review of the final version of *B-SMART* by EAB members. We project app development to occur in Months 1-7.

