**3C.7.3. Ancillary Measures.** CASAA Demographics Form: This form collects participant identification data and demographic information (e.g., age, education, sex, and ethnicity) about DWI offenders and CFMs. Items will be added to describe the relationship between the offender and CFM and the frequency of contact between them. System Usability Scale: This scale consists of ten Likert strongly agree to disagree items (Cronbach's alpha=.90) that asks the respondent to rate the technology product being reviewed (Example items: I think that I would like to use this product frequently; I found the product very awkward to use; I felt very confident using the product). Participants also provide a final overall rating of the product along a 7-point worst imaginable to best imaginable dimension.

**3C.7.4. Server-side Process Measures of Mobile Web App Performance and Use.** KB's programmers will create custom programs to track the implementation and use of the *B-SMART mobile web app*, as we have done for other technology-based and mobile interventions). The mobile web app will be hosted on KB's secure web server. Users will register and use a password to access the *B-SMART mobile web app* and this password will be used to track use, keeping data about users private. KB utilizes Microsoft SQL server for data collection of users; click-stream (pages visited), time on *B-SMART*, and number of individual visits.

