#### Concerned Family Member (CFM):

- male or female
- 21 years or older
- spouse, parent, or immediate family member of first-time DWI offender with IID installed in vehicle and enrolled in Santa Fe County DWI Program
- have a smartphone, tablet computer, or personal computer with Internet access
- consent to participate
- able to read and speak English or Spanish

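### App password recovery in 3C.6.3 relies on a personal question that the co-enrolled relative could probably answer, leaving the User ID as the only other stated barrier

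*Combined protocol and SAP*

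**What the plan says.** Section 3C.6.3 sets the rules for app accounts. On the account code: "Unique identifying user codes will be assigned to all first-time DWI offenders and their CFM by the research staff". Participants choose their own password. Both items are needed to get in: "The User ID and password will be used to access" the app, and the same pair labels the usage records. When the password is forgotten, "they will provide a unique answer to a standard personal question (e.g., what is your mother's first name"). A correct answer is all that the section asks for before the password is disclosed: "the mobile web app database will return the forgotten password". A user who has lost both the code and the password is sent to a technical hotline by telephone or email. The section does not say how the returned password is delivered. It describes no further check and no message to the owner.

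Section 3C.7.4 gives the password two jobs: "this password will be used to track use, keeping data about users private".

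On who holds the accounts, 2.2 Eligibility Criteria requires the concerned family member (CFM) to be a "spouse, parent, or immediate family member of first-time DWI offender with IID installed in vehicle", and 3C.6.2 enrols a pair only if both consent. Sections 3C.2 and 3.1.A also describe the CFM as living with the offender, although the lists in 2.2 and Figure 3 do not repeat this. Section 3C.5.1 adds: "CFMs will be able to share content with the DWI offender".

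**The concern.** A personal question gives some protection against strangers. In this trial the person most likely to be curious about an account is a close relative who is also a participant, and the one example given is a family fact. The recovery rule is therefore weakest against exactly the person with whom each account holder is paired.

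Two things are at stake. The first is confidentiality within the household: whatever a participant has typed and saved in the app could be read by the other member of the pair. The second is attribution. Pages visited, time and visits are logged by account, so a session opened with the other person's credentials is recorded under the wrong person with nothing to flag it. Those logs feed the exposure analysis in 3C.8.5 and its counterpart in the SAP.

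**Working it through.** The plan gives no figure on this point, so the check is textual apart from one count.

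1. **What opening an account takes.** 3C.6.3 requires the User ID and the password. The ID is unique and issued by staff. Nothing says that either member of a pair is given the other's ID.

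2. **What recovering the password takes.** One correct answer to a standard personal question. No second channel is described.

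3. **Who could answer.** Take the example question. If the CFM is the offender's mother, she is the answer. A father would know it, and a sibling will usually have the same mother. A spouse would probably know it. This is inference from the relationships in 2.2; the documents do not say what relatives know, and the mother's name is only an example.

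4. **What recovery implies about storage.** A system can return an existing password only if it holds it in a form that can be read back. This follows whatever the question and whatever the delivery route.

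5. **Whether another safeguard covers the gap.** The security text in 3.2.B lists encryption, firewalls, server access and login monitoring. These are directed at outside access. Neither the risk text in 3.1.B nor 3.2.B discusses access by the other member of the pair.

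6. **What sits behind the login.** The prototype module (3C.1.4) saved the user's typed entries on supportive things to say and do, and on words to use or avoid. 3C.5.1 carries that module into the full app, but the documents do not specify what the full app will save. Usage logs also sit behind the login (3C.7.4).

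7. **What does not.** Lockout events come from the DWI program database (3C.7.1). Survey responses are collected on a separate server (3.2.B) that is not said to share the app login. Hypothesis 1 and the survey-based mediators of Hypothesis 2 are therefore outside the problem.

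8. **Accounts under the rule.** 150 offenders + 150 CFMs in the intervention arm = 300 accounts at most.

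Steps 2 to 5 set against 3C.7.4 show the conflict: the password is said to keep data private, while its recovery rule is weak against the co-enrolled relative.

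**The case against.** The strongest reply is that the plan has a second barrier and leaves details open that could close the gap. A reader might infer that anyone who knows the family fact can open the account, or that each member of a pair can open the other's. The documents do not support that. The User ID is also needed, and someone without it is sent to staff. A shared home makes learning the ID plausible, but no document says that it is known or that devices are shared. The question finally used may differ from the example. If the password goes only to the owner's registered email or mobile number, most of the route is closed and the owner would see the message. All of this stands, and it limits the claim to a weak barrier.

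A reader might also want to count affected families. The documents give no rate of misuse, so any such count would be a guess.

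On consequences, the prototype's entries concern support and are not an account of a relative's drinking. 3C.5.1 encourages pairs to do activities together, so use by one account already mixes two people to some degree, and a better recovery rule does not cure that. The affected analysis is ancillary. These points also stand.

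Finally, this is a software detail in an app still under development, and data management procedures need IRB approval before the study begins. That lowers the urgency. It does not change the rule as written, which is a stated procedure and not merely an omitted one.

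**Conclusion.** The point holds as a minor one. 3C.6.3 states a recovery rule that a co-enrolled relative could probably satisfy, with the User ID as the only other stated barrier, and this undercuts the role that 3C.7.4 gives the password. Its reach is intervention-arm app accounts: saved entries, and person-level attribution of use in the ancillary exposure analysis. Confidentiality is the stronger ground; the effect on the exposure scores is likely to be marginal.

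The conclusion assumes that the question used resembles the example, that delivery is not restricted to the owner's own contact details, and that one member can learn the other's ID. If any of these is false, the exposure shrinks. The implication of readable storage does not depend on them. The statement that survey data are unaffected assumes that the survey server does not use the app login, as the text suggests.

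**What to change.** In 3C.6.3, replace the question-and-return rule with a one-time reset link sent to the participant's own registered email or mobile number, both of which the plan already uses to deliver the app link. Send the owner a notice whenever a reset is requested. Store passwords hashed, so that they cannot be returned. Log resets with dates, so that doubtful sessions can be flagged in the exposure analysis. Use the existing hotline as the fallback for participants without separate or accessible contact details, and state how staff confirm identity there, since no check is described now. Do not require the two members to have different contact details, because that could burden couples who share an email address.

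The cost is routine programming within the development phase and a sentence or two of protocol text, plus some hotline calls. A link opened on a shared device or in a shared mailbox would still be visible to the other person, so the change reduces the risk without removing it.
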